## **APPENDIX K: PROTOCOL CHANGES TO BE FOLLOWED DURING COVID-19 RESTRICTIONS**

### **OVERVIEW**

In response to the COVID-19 crisis, to ensure the safety of study subjects and Investigative Sites as well as proper conduct of the study, TEMPORARY changes to the protocol have been implemented. These changes should be followed only during COVID-19 restrictions and include extended IP administration windows, changes to masking rules, rescreening instructions, and a revised schedule of assessments.

Where feasible, sites could continue to follow the full schedule of assessments (based on their treatment group assignment).

### **EXTENDED IP ADMINISTRATION WINDOWS**

In order to allow more flexibility to sites and subjects, and to potentially mitigate missed IP administration, an extended IP administration window can be followed. The extended window can ONLY be used in situations related to COVID-19 restrictions and after medical monitor approval. Footnote “T” of each COVID-19 assessment table below reflects these extended IP options.

Per protocol, the IP administration window is as follows:

- Monthly treatment group: +/- 8 days for the entire study duration
- EOM treatment group: +/- 8 days for the first study year and +/- 16 days for the second study year

During COVID-19 restrictions, the IP administration window can be extended to the following:

- Monthly treatment group: -8 days to +15 days. Note, interval for consecutive injections must be at least 14 days.
- EOM treatment group: -8 days to +30 days for the first study year and -16 days to +30 days for the second study year.

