## 8. STUDY PROCEDURES

A study schema is presented below in [Figure 1](#). All randomized subjects will return every month to the clinical site for assessments and additional pegcetacoplan or sham injections according to their randomization scheme until Month 12. From Month 12 onwards, subjects will return to the clinical site based on their randomized treatment schedule (monthly or EOM) and will follow the treatment regimen and assessments outlined in the Visit Schedule until Month 24. In addition, subjects will be contacted via phone by masked study staff 4 ( $\pm 2$ ) days after the first 3 study treatments to collect safety information.

The end of this trial for each subject is defined as when the subject completes their Month 24 study visit, approximately 30 days (monthly treatment group) and approximately 60 days (EOM treatment group) after the last visit at which IP is administered. The period following last dose of IP is sufficient to evaluate the safety of pegcetacoplan based on its half-life in the vitreous; further details can be found in the pegcetacoplan IB. At the end of the 24-month study period, subjects will be offered entry to enroll into a separate open-label study.

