The completion of the 24-month study period occurs approximately 30 days (monthly treatment group) and approximately 60 days (EOM treatment group) after the last visit at which IP is administered. The period following last dose of IP is sufficient to evaluate the safety of pegcetacoplan based on its half-life in the vitreous; further details can be found in the pegcetacoplan IB. At the end of the 24-month study period, subjects will have the option to enroll into a separate open-label study.

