### 11.2. Recording Adverse Events

Adverse events and SAEs will be collected from the signing of the consent form until the last visit or early termination visit, 30 days after the last IP administration for the monthly treatment groups and 60 days after the last IP administration for the EOM treatment groups.

Any events that occur prior to dosing will be categorized as pretreatment events; events occurring after dosing will be recorded as TEAEs (start date of dosing and, therefore, categorization of the event will be dependent on randomization assignment).

For each AE, the investigator will evaluate and report the onset date (and time if applicable), resolution date (and time if applicable), intensity, causality, action taken, serious outcome, and whether or not it caused the subject to discontinue the study.

If possible, the outcome of any AE that caused permanent discontinuation or was present at the end of the study should be reported, particularly if the AE was considered by the investigator to be related to the IP. Subjects experiencing AEs that cause interruption or discontinuation of IP, or those experiencing AEs that are present at the last visit or early termination visit should receive follow-up as appropriate.

All SAEs must be reported to the sponsor/Apellis Safety via eCRF within 24 hours of becoming aware of the event, whether or not the event is deemed treatment-related. If the electronic data capture (EDC) system is not operational (or for paper-based study[ies]), the site must complete the paper SAE form and email to CCI immediately and also within 24 hours of becoming aware of the event. The reported information submitted as a paper SAE must be entered into the EDC system once it becomes operational.

Adverse events will be coded in accordance with the Medical Dictionary for Regulatory Activities (MedDRA). If known, the diagnosis of the underlying illness or disorder should be recorded, rather than its individual symptoms.

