### 12.8. Safety Analyses

Adverse events will be collected from the time of the first study drug administration until a subject completes the study or discontinues prematurely. Treatment-emergent adverse events are defined as those AEs that develop or worsen after the first dose of study medication and up to 30 days beyond the last dose of study medication. The current version of MedDRA will be used to classify all AEs. Treatment-emergent AEs will be summarized by System Organ Class and Preferred Term, in accordance with the MedDRA coding dictionary. The number of subjects reporting each AE Preferred Term will be tabulated for all TEAEs and separately for those considered as related to study treatment by the investigator or designee. Number of subjects reporting SAEs will also be tabulated. Adverse event summaries will be presented for each treatment group separately.

Adverse events will be summarized by MedDRA coding terms, and separate tabulations also will be produced for related AEs (those considered by the investigator as definitively drug related), SAEs, and discontinuations due to AEs. Vital signs data and findings from physical and ophthalmologic examinations will be tabulated for changes over time on study. Laboratory parameters will be summarized for changes across study by using descriptive statistics. Separate summaries will be prepared for systemic (nonocular) and ocular AEs, with events in the study eye and nonstudy eye summarized separately.

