A. For subjects that discontinue the study early, the early termination assessments should be performed after a minimum of 30 days have passed from the last dosing visit. If a subject reports for a scheduled visit and decides to terminate early prior to dosing, the visit should be considered the early termination visit and all early termination procedures should be performed. At Month 24, all subjects should be offered entry into an open-label study.

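### A scheduled final dose given in the days added by the COVID-19 extension cannot be followed by an in-window Month 24 visit at the stated 30 or 60 days; completers have no minimum AE follow-up

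*Protocol*

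**What the plan says.** Protocol Section 11.2 collects AEs and SAEs from consent "until the last visit or early termination visit, 30 days after the last IP administration for the monthly treatment groups". For EOM, the same sentence puts the end of collection at "60 days after the last IP administration for the EOM treatment groups". Section 8 places the Month 24 visit "approximately 30 days (monthly treatment group) and approximately 60 days (EOM treatment group) after the last visit at which IP is administered", and the synopsis also says approximately. Section 8.1.4.2 adds: "The period following last dose of IP is sufficient to evaluate the safety of pegcetacoplan based on its half-life in the vitreous". That section also states that nothing is injected at Month 24.

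Appendix K, Extended IP Administration Windows, widens the dosing window during COVID-19 restrictions, with medical monitor approval. For the monthly group: "Monthly treatment group: -8 days to +15 days. Note, interval for consecutive injections must be at least 14 days". The corresponding rule for the other regimen reads: "EOM treatment group: -8 days to +30 days for the first study year and -16 days to +30 days for the second study year". The COVID-19 visit schedules in Appendix K keep Month 24 at Day 720, ±8 days (monthly) or ±16 days (EOM), with visits projected from the Day 1 visit date.

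Two other places use 30 days as the benchmark for all arms. Section 12.8 counts TEAEs "up to 30 days beyond the last dose of study medication". Footnote A of the visit schedules, EOM included, says that for subjects who leave early "the early termination assessments should be performed after a minimum of 30 days have passed from the last dosing visit".

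**The concern.** Appendix K moves the dose but not the visit that closes safety collection. A late final dose therefore eats into the follow-up that Sections 8 and 11.2 describe, and that Section 8.1.4.2 calls sufficient.

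No other rule closes the gap:

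- The 14-day rule covers consecutive injections, and no injection follows the last one.
- Footnote A protects early terminators, and Section 6.5 lets their procedures fall outside the window. A completer has no stated minimum, so can receive less follow-up than a subject who leaves.
- Section 11.5 follows events already present at exit, not new ones.
- Section 11.2 does not say whether the visit or the 30/60 days governs when the two differ.

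At stake are new-onset events in the weeks after the last injection, in subjects who do not go straight into the open-label study.

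**Working it through.** **Inputs**

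- Last scheduled dose: Day 690 (Month 23, monthly) and Day 660 (Month 22, EOM), from the visit schedules and Section 8.1.4.2. The injection counts in Table 1 agree: Day 1 plus Months 1 to 23 is 24; Day 1 plus even months 2 to 22 is 12. The monthly Month 13–24 tables, as read from the PDF, show an injection mark at Month 24. I follow the text and Table 1.
- Month 24 window: Days 712–728 (monthly) and 704–736 (EOM).
- Ordinary dosing window: ±8 days (monthly), ±16 days (EOM, second year).
- Appendix K upper limit: +15 days (monthly), +30 days (EOM).

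Follow-up = day of Month 24 visit − day of last dose.

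**The plan's own figures.** On target days, 720 − 690 = 30 and 720 − 660 = 60. Both are reproduced.

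**Ordinary windows**

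- Monthly: doses on Days 682–698. Adding 30 gives Days 712–728, exactly the visit window, so 30 days is always attainable. The minimum is 712 − 698 = 14 and the maximum 728 − 682 = 46.
- EOM: doses on Days 644–676. Adding 60 gives Days 704–736, again exactly the visit window. The minimum is 704 − 676 = 28 and the maximum 736 − 644 = 92.

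**Days added by Appendix K**

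- Monthly, +9 to +15: Days 699–705. The 30-day mark is 699 + 30 = 729 to 705 + 30 = 735, after the window closes on Day 728.
- EOM, +17 to +30: Days 677–690. The 60-day mark is 677 + 60 = 737 to 690 + 60 = 750, after Day 736.

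| Exit | Monthly, dose Day 699 to 705 | EOM, dose Day 677 to 690 |
|---|---|---|
| Earliest in window | 712 − 699 = 13 to 712 − 705 = 7 | 704 − 677 = 27 to 704 − 690 = 14 |
| Day 720 | 720 − 699 = 21 to 720 − 705 = 15 | 720 − 677 = 43 to 720 − 690 = 30 |
| Latest in window | 728 − 699 = 29 to 728 − 705 = 23 | 736 − 677 = 59 to 736 − 690 = 46 |

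The monthly range is 7–29 days, below 30 throughout. The EOM range is 14–59 days, below 60 throughout. The EOM 30-day mark is 677 + 30 = 707 to 690 + 30 = 720, so EOM falls below 30 only with an exit before Day 707 to before Day 720, depending on the dose day.

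**If the scheduled final dose is skipped** and the dose before it was the extended one:

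- Monthly, Month 22 dose on Days 669–675: 712 − 675 = 37 to 728 − 669 = 59, above 30.
- EOM, Month 20 dose on Days 617–630: 704 − 630 = 74 to 736 − 617 = 119, above 60.

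The shortfall does not arise in these cases.

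**The case against.** **The interval is approximate.** Section 8, Section 8.1.4.2 and the synopsis all say so; only Section 11.2 is unqualified. This disposes of a shortfall of a few days, such as 1 to 7 days at the latest in-window monthly exit. It does not stretch to 15–21 days when the visit is exactly on time.

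**Section 11.2 can be read so that the interval governs**, in which case collection continues past the visit and nothing is lost. That reading is open, but no contact is scheduled to carry it out.

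**Safeguards exist.** Each extension needs a COVID-19 reason and medical monitor approval, events present at exit are followed, and an open-label study is offered. All true, but none of these captures a new event in a subject who declines the open-label study.

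**Appendix K is not the only cause.** This stands. Ordinary windows already allow 14 days (monthly) or 28 days (EOM), because Month 24 is tied to Day 1. Appendix K only removes the possibility of meeting 30/60 within the window.

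**Thirty days may be enough for EOM.** Largely accepted: the protocol treats about 30 days as sufficient after the same 15 mg dose given monthly, and Section 12.8 and footnote A apply 30 days to EOM as well.

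A reader might infer three stronger things. One is that any use of the extension shortens follow-up; the skipped-dose case and doses still inside the ordinary window show otherwise. Another is that EOM subjects generally drop below 30 days; with exit on Day 720 or later they do not. The third is that the follow-up is clinically inadequate. The protocol rests adequacy on vitreous half-life and refers to the investigator's brochure, so these documents cannot settle it.

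**Conclusion.** The inconsistency is real and narrow. It holds when the dose actually last given is the Month 23 (monthly) or Month 22 (EOM) dose, it falls on Days 699–705 or 677–690, and the subject completes with a Month 24 visit inside its window. Every such monthly subject then has less than 30 days of follow-up. Every such EOM subject has less than the stated 60, but at least 30 unless exit comes before Day 720.

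The wider weakness is that completers have no stated minimum interval, which also matters under ordinary windows.

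Materiality is low. The documents do not give the number of subjects concerned, and it may be zero. The primary endpoint is untouched, and the TEAE definition in SAP Section 7.1 has no upper time limit, so it does not change. Only new events after exit could go unrecorded. Severity: optional.

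**What to change.** State in Section 11.2, with a cross-reference in Appendix K, that any completer whose Month 24 visit falls less than 30 days after the last IP administration gets one telephone AE/SAE contact at 30 days after that dose. This should apply whether or not the extension was used, and be waived if AE/SAE collection has already begun in the open-label study. Triggering on the interval matters: a rule tied to the extension would call a subject with 29 days and miss one with 14 under ordinary windows.

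For EOM, also state in Sections 8 and 11.2 that a final dose given in the added days leaves less than 60 days, and at least 30 with exit on Day 720 or later.

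Leave dosing windows, Month 24 assessments and analyses as they are. The cost is a few sentences and one telephone call per subject concerned, of a kind that Appendix K already uses for missed visits.

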### **MASKING RULES**

Due to current COVID-19 restrictions, clinical sites might encounter difficulties maintaining appropriate clinic staffing to satisfy the approved masking rules for the APL2-303 (Derby) study. Based on this, and in an attempt to minimize the amount of missed data and IP administrations, Apellis is implementing a temporary adjustment to the study masking rules.

This temporary change must be approved by the Apellis Medical Director **prior to** implementation and must be documented via a temporary and modified delegation of authority Log. Each masked assessment performed by an unmasked staff and vice versa (even with Apellis approval and following the below guidelines) should be documented.

The principal investigator (PI) is responsible for the overall oversight of the study site data and s/he will not be allowed to switch into an unmasked role. Every masked individual that performs IP administration and/or postinjection assessment (all unmasked assessment) as a temporary measure, will **permanently** be considered an unmasked individual and will not be able to perform masked assessments once these exemptions are lifted.

## **RESCREENING PROCEDURE**

Prior to the implementation of these temporary changes, sites continuing to screen patients have been encouraged to complete the screening and baseline assessments in their entirety. However, if a subject was deemed a screen failure for not being able to meet the original screening window (Day -28 to Day -1 [+/- 2 days]) due to COVID-19 related restrictions, a rescreening visit is allowed and should be followed according to the 2 scenarios below.

### **Subjects Who Completed Screening and Were Considered Eligible by Reading Center and Investigator**

Subjects who were screened prior to 30 March 2020 and completed all screening assessments (as described in the Schedule of Assessments [Appendix A](#) [every month treatment group] and [Appendix C](#) [every other month [EOM] treatment group]) and considered eligible by the reading center and investigator and are able to return to the clinic within 90 days of initial screening, will receive a new subject ID number and undergo an *abbreviated screening*, prior to randomization, that includes the following assessments:

- Informed consent/assign new screening number
- Normal luminance best corrected visual acuity assessment
- Slitlamp examination
- Dilated indirect ophthalmoscopy
- IOP measurement
- SD-OCT\*
- Concomitant medication/concomitant ocular procedures collection
- AE collection

\*SD-OCT images collected at this visit will not be used by the reading center to determine eligibility but should be used by the investigator to detect any potential new exclusion criterion.

If the investigator deems it necessary, additional assessments can be performed if there is a concern that the subject might now meet an exclusion criterion that was not the case during the original screening (eg, FFA to exclude the presence of CNV).

### **Subjects With Incomplete Screening Assessment**

Subjects that signed the informed consent but were not able to complete all screening assessments due to COVID-19-related restrictions are not eligible for the abbreviated screening. These subjects can be rescreened but must follow the standard screening schedule of assessment (as described in the Schedule of Assessments [Appendix A](#) [every month treatment group] and [Appendix C](#) [EOM treatment group]). These subjects will also receive a new screening ID number.

## **MINIMUM SCHEDULE OF ASSESSMENT**

### **Schedule of Assessments**

Where feasible, sites could continue to follow the full schedule of assessments (based on their treatment group assignment). The minimum assessment tables, only to be followed during this

COVID-19 effort and if determined necessary to use based on the investigator's clinical judgment, are provided below to reduce the time required for each study visit. Subjects in the EOM treatment group do not need to be seen for the non-IP administration visits. Assessments not performed (even those that have been removed in the minimum assessment table) should be documented.

Subjects that are not able to come into the clinic for a study visit due to COVID-19-related restrictions, including visits for the EOM group that do not include IP administration, should be contacted via the phone for the collection of AEs (including SAEs) and concomitant medications. **All SAEs are still required to be reported to Apellis within 24 hours of site awareness, even if reported via phone call.** All communications via phone call should also be documented in the source documents and in the respective CRF page. In addition, these subjects should be instructed to self-monitor their vision at home and report any changes in vision or their overall health via phone call. The site must inform the Sponsor of any subjects lost to follow-up.

It is critical that local, country, and regional governance regarding COVID-19 is followed along with your best clinical judgment when managing this situation. All visits or assessments missed as a result of COVID-19 will be captured in the case report forms.

The Schedule of Assessments tables shown below supersede those sent on 30 March 2020. These changes were previously communicated to the sites via a memorandum.

**APPENDIX A (TRACKED): COVID-19 VISIT SCHEDULE—Monthly Group—Screening, Day 1 Through Month 12**

Visit #	Screening	Treatment														Early Term A
	1	2	2A	3	4	5	6	7	8	9	10	11	12	13	14	
Day	-28 to -1	1	7	30	60	90	120	150	180	210	240	270	300	330	360	
Week	0	0	1	4	8	12	16	20	24	28	32	36	40	44	48	
Month	0	0	0	1	2	3	4	5	6	7	8	9	10	11	12	
Window (+ or - days)	2	0	1	8	8	8	8	8	8	8	8	8	8	8	8	
Informed Consent/Assign Screening Number	x															
Demographic Data	x															
Inclusion/Exclusion Criteria B	x	x														
Medical/Surgical/Ocular History C	x															
Blood Draw—Safety Labs D,E,F	x	x			*				*						x	x
Urine Sample Collection D,E,F	x	x			*				*						x	x
Urine Pregnancy Test D,E,F		x		x	x	x	x	x	x	x	x	x	x	x	x	
Blood Draw—PK and Complement Profile (C3, CH50, AH50) D,S		x	x	x					x						x	x
Blood Draw—Genotyping (if applicable) D					*											
Blood Draw- Anti-Pegcetacoplan Ab D		x		*	*				*						x	x
Blood Draw for Clinical Repository (if applicable) D,G					*				*						*	*
Vital Signs H	x	x		*	*	*	*	*	x	*	*	*	*	*	x	x
Physical Examination I	x														x	x
BCVA J	x	x		x	x	x	x	x	x	x	x	x	x	x	x	x
LL-BCVA J		x		*	*	*	*	*	x	*	*	*	*	*	x	x
MNREAD or Radner Reading Charts (select countries) J,K		x							*						x	x
Slitlamp Examination	x	x		x	x	x	x	x	x	x	x	x	x	x	x	x
Endothelial Cell Count S		x							x						x	x
NEI VFQ-25 L		x							*						x	x

**APPENDIX A (TRACKED): COVID-19 VISIT SCHEDULE—Monthly Group—Screening, Day 1 Through Month 12**

	Screening	Treatment														Early Term A
Visit #	1	2	2A	3	4	5	6	7	8	9	10	11	12	13	14	
Day	-28 to -1	1	7	30	60	90	120	150	180	210	240	270	300	330	360	
Week	0	0	1	4	8	12	16	20	24	28	32	36	40	44	48	
Month	0	0	0	1	2	3	4	5	6	7	8	9	10	11	12	
Window (+ or - days)	2	0	1	8	8	8	8	8	8	8	8	8	8	8	8	
FRI L		x							*						x	x
Home-Based Digital Applications LMS		x		*	*	*			*						x	
Dilated Indirect Ophthalmoscopy	x	x		x	x	x	x	x	x	x	x	x	x	x	x	x
IOP Measurement	x	x		x	x	x	x	x	x	x	x	x	x	x	x	x
SD-OCT N	x	x		*	*	*	*	*	x	*	*	*	*	*	x	x
FAF N	x	x			SE		SE		x		SE		SE		x	x
NIR N	x	x			SE		SE		x		SE		SE		x	x
DCFP N	x														x	x
FFA N	x														x	x
OCT-A RS		x R							* R						x R	x
Study Eye Determination	x															
Randomization		x														
Pegcetacoplan administration or Sham Injection T		x		x	x	x	x	x	x	x	x	x	x	x	x	
Postinjection Assessment O		x		x	x	x	x	x	x	x	x	x	x	x	x	
Follow-Up Call P		x		x	x	x										
Concomitant Medication/Concomitant Ocular Procedures Q	x	x	*	x	x	x	x	x	x	x	x	x	x	x	x	x
Adverse Events	x	x	*	x	x	x	x	x	x	x	x	x	x	x	x	x

## APPENDIX A (TRACKED): COVID-19 VISIT SCHEDULE—Monthly Group—Screening, Day 1 Through Month 12

Abbreviations: AH50 = alternative pathway of complement functional test; BCVA = best corrected visual acuity; CH50 = classical pathway of complement functional test; CNV = choroidal neovascularization; DCFP = digital color fundus photography; eCRF = electronic case report form; FAF = fundus autofluorescence; FFA = fundus fluorescein angiography; FRI = Functional Reading Independence Index; IOP = intraocular pressure; LL-BCVA = low luminance best corrected visual acuity; MNREAD = Minnesota Low-Vision Reading Test; NEI VFG-25 = National Eye Institute Visual Functioning Questionnaire 25-Item Version; NIR = near infrared reflectance; OCT-A = optical coherence tomography angiography; PK = pharmacokinetics; SD-OCT = spectral domain optical coherence tomography; SE = study eye; Term = termination; VEGF = vascular endothelial growth factor.

Note: All ocular assessments are to be performed for both eyes unless annotated with 'SE' (study eye) in the above schedule. All assessments should be performed on the same day.

All study visits should be scheduled and projected based on the Day 1 visit date with the exception of Visit 2a which should be based on the Day 1 dose date.

- A. For subjects that discontinue the study early, the early termination assessments should be performed after a minimum of 30 days have passed from the last dosing visit. If a subject reports for a scheduled visit and decides to terminate early prior to dosing, the visit should be considered the early termination visit and all early termination procedures should be performed. At Month 24, all subjects should be offered entry into an open-label study.
- B. At Day 1 (Visit 2), confirm subject eligibility through reviewing the inclusion/exclusion criteria and receive confirmation of eligibility from the reading center.
- C. Significant medical/surgical history from the previous 5 years. Anti-VEGF treatments (fellow eye) and invasive ocular procedures performed within the past 5 years and while on study should also be recorded. Any history of tobacco use should be recorded.
- D. Obtain prior to fluorescein angiography and before study drug administration.
- E. At screening, serum pregnancy should be performed for women of childbearing potential. If positive, subject is not eligible to continue in the study.
- F. Beginning at Day 1, perform the urine pregnancy test for women of childbearing potential at each treatment visit. If positive, perform a serum pregnancy test. If serum test is positive, study drug should not be administered and an early term visit should be completed.
- G. Only subjects that sign the separate consent for the clinical repository and genotyping will have these samples collected. A 14-mL whole-blood sample will be collected at each of the specified visits.
- H. Blood pressure, respiratory rate, heart rate, and temperature. On dosing days, vital signs should be taken predose.
- I. Height and weight should be collected at screening.
- J. Perform assessments prior to dilating the eyes.
- K. In select countries, the MNREAD or Radner Reading Charts should be done during the study visit, prior to dilating the eyes. It should be performed monocularly first, then binocularly.
- L. To be administered by the masked site staff prior to any other assessments performed on that day. In-clinic assessments on the digital application should be completed after completion of all functional tests and quality of life measures prior to dilating the eyes.
- M. At select sites, and for those subjects who decide to participate, the digital applications will be completed on an electronic device and will consist of assessments for visual function and reading speed. Subjects will receive training at Day 1 on the use of the digital applications and the electronic device and will perform the tests using the application in the clinic at Month 1, Month 2, Month 3, Month 6, Month 12, Month 18, and Month 24. Beginning at Day 1, subjects will complete the functional assessments weekly at home. Subjects should be instructed to complete the assessments on the same day each week and at approximately the same time of day each week, if possible.
- N. FAF and SD-OCT images, near infrared reflectance, fluorescein angiograms, and fundus photographs will be performed for the study eye only on days where 'SE' is specified and for both eyes at all other visits as specified in the above schedule and will be sent to the reading center for evaluation (consult the reading center manual for specifics on image capture, processing, and transmission). Images should be captured prior to dosing on dosing days. If a subject misses a study visit or images cannot be obtained at a specific visit, study staff should make every effort to obtain images at the next scheduled visit. If new active CNV is suspected, SD-OCT, FFA, and OCT-A (select sites) images must be collected and sent to the reading center for analysis.
- O. Postinjection assessments should be performed within 5 minutes after dosing by the unmasked physician or study staff and should include a gross assessment of vision (finger-counting, hand motion, then light perception when applicable). If subject passes gross vision test, the subject may leave the site. If subject fails gross vision test, the tonometry should be performed. IOP should be  $\leq 30$  mm Hg in order for the subject to leave the site. If necessary, antiglaucomatous medication can be given to lower the IOP. If IOP is  $>30$  mm Hg, assessments will continue every approximately 30 minutes from the previous measurement until the subject passes gross vision test and IOP is  $\leq 30$  mm Hg. Note: if the study eye is treated with a ranibizumab or aflibercept injection during the same visit as the study treatment (pegcetacoplan or sham), the treatment with ranibizumab or aflibercept must be performed first. The pre- and post- anti-VEGF IOP values must be measured and recorded on the eCRF.

